3.3.2. Benefit Assessment

Given gepotidacin's spectrum of activity against *E. coli*, *S. saprophyticus*, and *E. faecalis*, as well as human safety data and the pharmacokinetic (PK) profile, it is anticipated that gepotidacin will benefit participants with acute cystitis.

Overall, all participants in this study will not only receive routine medical monitoring appropriate for acute cystitis, but they will also receive heightened monitoring to ensure safety when participating in a clinical study.

The PK data from this study will be used to support the indication for gepotidacin as a potential new treatment option for acute cystitis.

3.3.3. Overall Benefit:Risk Conclusion

Together with the known preclinical data for gepotidacin against *E. coli*, *S. saprophyticus*, and *E. faecalis*, cumulative safety results from Phase I and Phase II studies with oral gepotidacin treatment, and the PK data from this study will be used to support the indication for gepotidacin as a potential new treatment option for acute cystitis.

None of the potential or identified risks seen to date in participants dosed with gepotidacin preclude further clinical development. Mitigation strategies have been implemented to promptly identify and appropriately address risks in order to protect participant safety and to better characterize the safety profile of the study treatment (Section 3.3.1), including additional 12-lead ECG assessments during the study while participants are confined. Careful safety monitoring should also identify any emerging safety issues for gepotidacin and contribute to further benefit-risk profile development.

The investigator may, at his or her discretion, discontinue the participant from study treatment at any time and initiate appropriate alternative therapy.

Taking into account the measures taken to minimize risk to participants participating in this study, the potential risks identified in association with gepotidacin are justified by the anticipated benefits that may be afforded to participants with acute cystitis.

4. OBJECTIVES AND ENDPOINTS

Objectives	Endpoints

Primary
 
 To determine the plasma PK parameters of gepotidacin following repeat oral doses of gepotidacin (1500 mg [2 × 750-mg tablets] twice daily [BID] for 5 days) in adult female participants with acute cystitis 	
 Plasma gepotidacin area under the concentration-time curve (AUC) from zero (predose) over the dosing interval (AUC[0-τ]), maximum plasma concentration (C_{max}), and time of occurrence of C_{max} (t_{max}) on Days 1 and 4 and apparent steady state clearance (CL_{ss}/F) and accumulation ratio (R_o) on Day 4 Plasma predose concentration (C_τ) of gepotidacin on Days 1 through 5

Secondary
 
 To determine the urine PK parameters of gepotidacin following repeat oral doses of gepotidacin in adult female participants with acute cystitis 	
 Urine gepotidacin amount of drug excreted over 12 hours (A_e 12h), amount of drug excreted in urine in a time interval (A_e[t₁-t₂]), percentage of the given dose of drug excreted in urine (fe%), and renal clearance (CL_r) of gepotidacin on Days 1 and 4 Urine predose concentration (C_τ) on Days 1 through 5

 To assess the safety and tolerability of repeat oral doses of gepotidacin in adult female participants with acute cystitis 	
 Treatment-emergent AEs and serious AEs and change from baseline results for physical examinations, vital sign measurements, electrocardiograms (ECGs), and clinical laboratory tests

Exploratory
 
 To explore the combined clinical and microbiological efficacy of gepotidacin in adult female participants with acute cystitis who have a qualifying baseline uropathogen 	
 Therapeutic response (combined per-participant microbiological and clinical response) at the Test-of-Cure (TOC) Visit

 To assess time to eradication of uropathogens in adult female participants with acute cystitis who have a qualifying baseline uropathogen 	
 Microbiological outcome on Days 2 through 5; Microbiological outcome and response at the TOC and Follow-up Visits

 To explore time to resolution of signs and symptoms in adult female participants with acute cystitis 	
 Clinical outcome on Days 2 through 5; Clinical outcome and response at the TOC and Follow-up Visits

 To assess the relapse rate (microbiological and clinical) of acute cystitis after treatment with gepotidacin in adult female participants with acute cystitis at the Follow-up Visit 	
 Therapeutic response (combined per-participant microbiological and clinical response) at the Follow-up Visit

Objectives	Endpoints

 To explore the microbiological and antimicrobial susceptibility profile of uropathogens recovered from adult female participants with acute cystitis, including subsets of isolates resistant to other antimicrobials 	
 Gram stain, quantitative bacteriology culture, and in vitro antimicrobial susceptibility test results at Baseline, Days 2 through 5, and at the TOC and Follow-up Visits

 To explore gepotidacin plasma PK/pharmacodynamic (PD) relationships in adult female participants with acute cystitis 	
 Relationship between gepotidacin exposure and clinical and microbiological response, if data permit

 To explore the distribution of gepotidacin in cervical, rectal, and pharyngeal tissue (swab specimens) 	
 Gepotidacin concentration in cervical, rectal, and pharyngeal tissues, if data permit

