
 Any participant that receives administration of an alternative or additional antibacterial therapy before the Follow-up Visit will be assigned a microbiological outcome of “unable to determine” and a response of “microbiological failure.” Participants considered microbiological failures at the TOC Visit will also be considered microbiological failures at the Follow-up Visit. 		
A quantitative urine culture taken at the Follow-up Visit shows reduction of the qualifying bacterial uropathogen recovered at Baseline to $<10^3$ CFU/mL	Sustained microbiological eradication	Microbiological success
A quantitative urine culture taken at the Follow-up Visit shows that the qualifying bacterial uropathogen recovered at Baseline grows $\geq 10^3$ CFU/mL	Microbiological recurrence	Microbiological failure
A determination of the baseline qualifying bacterial uropathogen microbiological response cannot be made (e.g., no urine culture taken, sample lost, etc.)	Unable to determine	Microbiological failure
A new qualifying bacterial uropathogen, not identified at Baseline, is documented by quantitative urine culture at the Follow-up Visit in a participant who is a clinical failure	New infection	Microbiological failure
A new qualifying bacterial uropathogen, not identified at Baseline, is documented by quantitative urine culture at the Follow-up Visit in a participant who is a clinical success	Colonization	Microbiological success

CFU=colony-forming units; TOC=Test-of-Cure.

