Persistence of signs and symptoms of infection, reappearance of signs and symptoms, or use of other antimicrobial therapy for the current infection Participants considered clinical failures at the TOC Visit will also be considered clinical failures at the Follow-up Visit.	Clinical failure	Failure
Refusal to consent to a clinical examination or failed to attend the TOC Visit	Unable to determine	Failure

Defining Criteria	Outcome (Investigator-Determined) ^a	Response
Follow-up Visit		
Resolution of signs and symptoms of acute cystitis demonstrated at the TOC Visit persist at the Follow-up Visit (and no new signs and symptoms) and no use of other antimicrobial therapy	Sustained clinical success	Success
Persistence of signs and symptoms of infection, reappearance of signs and symptoms, or use of other antimicrobial therapy for the current infection	Clinical failure	Failure
Signs and symptoms of acute cystitis absent at the TOC Visit re-occur at the Follow-up Visit and no use of other antimicrobial therapy	Clinical recurrence	Failure
Refusal to consent to a clinical examination or failed to attend the Follow-up Visit	Unable to determine	Failure

TOC=Test-of-Cure.

- a. The investigator will determine the clinical outcome by comparing the signs and symptoms of acute cystitis at the On-Therapy (Days 2 through 5 only), TOC, and Follow-up Visits) to those present at Baseline.
- b. A participant showing some improvement at the On-Therapy Visit (Days 2 through 5 only) but less than what would be considered a clinical success should remain on study treatment per protocol, but study treatment may be discontinued per predefined criteria (see Section 8.1) or if there has been no clinical improvement; study treatment may be replaced by a different antibiotic, at the discretion of the investigator.

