10.3.3. Exploratory Analyses

Endpoint	Statistical Analysis Methods
Exploratory	
 Therapeutic response (number and percentage of participants with combined per-participant microbiological and clinical response) will be summarized by pathogen at the TOC Visit for the micro-ITT Population. The microbiological outcome and response (number and percentage of participants with microbiological success) will be summarized by pathogen group on Days 2 through 5 (outcome only) and at the TOC and Follow-up Visits for the micro-ITT Population. The clinical outcome and response (number and percentage of participants with resolution of signs and symptoms) will be summarized by pathogen group on Days 2 through 5 (outcome only) and at the TOC and Follow-up Visits for the micro-ITT Population. Therapeutic response (number and percentage of participants with combined per-participant microbiological and clinical response) at the Follow-up Visit for the micro-ITT Population. Gram stain, quantitative bacteriology culture, and in vitro antibacterial susceptibility testing results for urine specimens will be summarized at the Baseline Visit (predose on Day 1), on Days 2 through 5, and at the TOC and Follow-up Visits for the micro-ITT Population. The PK/PD relationship between gepotidacin exposure and microbiological and clinical outcome and/or response at the On-Therapy, TOC, and Follow-up Visits may be explored, if data permit. This may include assessment of gepotidacin exposures correlated with baseline minimum inhibitory concentrations and/or decreases in the baseline pathogen CFU/mL. Gepotidacin concentrations in cervical, rectal, and pharyngeal tissues will be summarized, if data permit.

The PK/PD exploratory analyses will be described in the RAP and may be presented separately from the main clinical study report.

Stool, vaginal, and pharyngeal microbiome specimens may be analyzed to assess the number and proportion of relevant bacterial populations and metabolomics, as data permit. This analysis may be presented separately from the main clinical study report.

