
 To explore time to resolution of signs and symptoms in adult female participants with acute cystitis 	
 Investigator-determined clinical outcome on Days 2 through 5, TOC, and Follow-up Visits Sponsor-determined clinical outcome on Days 2 through 5; sponsor-determined clinical outcome and response at the TOC and Follow-up Visits

 To assess the relapse rate (microbiological and clinical) of acute cystitis after treatment with gepotidacin in adult female participants with acute cystitis at the Follow-up Visit 	
 Therapeutic response (combined per-participant microbiological and clinical response) at the Follow-up Visit

[figure not shown]
Objectives	Endpoints

To explore the microbiological and antimicrobial susceptibility profile of uropathogens recovered from adult female participants with acute cystitis, including subsets of isolates resistant to other antimicrobials	
Gram stain, quantitative bacteriology culture, and in vitro antimicrobial susceptibility test results at Baseline, Days 2 through 5, TOC, and Follow-up Visits

To explore gepotidacin plasma PK/pharmacodynamic (PD) relationships in adult female participants with acute cystitis	
Relationship between gepotidacin exposure and clinical and microbiological response, if data permit

To explore the distribution of gepotidacin in cervical, rectal, and pharyngeal tissue (swab specimens)	
Gepotidacin concentration in cervical, rectal, and pharyngeal tissues, if data permit

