Table 6 Microbiological Outcome and Response by Qualifying Uropathogen at the Follow-Up Visit

Defining Criteria	Outcome	Response

 Any participant that receives administration of an alternative or additional antibacterial therapy before the Follow-up Visit will be assigned a microbiological outcome of “unable to determine” and a response of “microbiological failure”. Participants considered microbiological failures at the TOC Visit will also be considered microbiological failures at the Follow-up Visit. 		

 A quantitative urine culture taken at the Follow-up Visit shows reduction of the qualifying bacterial uropathogen recovered at Baseline to $<10^3$ CFU/mL 	
 Sustained microbiological eradication 	
 Microbiological success

 A quantitative urine culture taken at the Follow-up Visit shows that the qualifying bacterial uropathogen recovered at Baseline grows $\geq 10^3$ CFU/mL 	
 Microbiological recurrence 	
 Microbiological failure

 A determination of the baseline qualifying bacterial uropathogen microbiological response cannot be made (e.g., no urine culture taken, sample lost, etc.) 	
 Unable to determine 	
 Microbiological failure

 A new qualifying bacterial uropathogen, not identified at Baseline, is documented by quantitative urine culture at the Follow-up Visit in a participant who is a sponsor-determined clinical failure 	
 New infection 	
 Microbiological failure

 A new qualifying bacterial uropathogen, not identified at Baseline, is documented by quantitative urine culture at the Follow-up Visit in a participant who is a sponsor-determined clinical success 	
 Colonization 	
 Microbiological success

CFU=colony-forming units; TOC=Test-of-Cure.

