
 • Refusal to consent to a clinical examination or failure to attend the On-Therapy visit (Days 2 through 5 only) 	
 • Unable to Determine 	
 • Not applicable
Test-of-Cure Visit		

 • Resolution of signs and symptoms of acute cystitis (total cumulative score is zero) present at Baseline (and no new signs or symptoms) and no use of other antimicrobial therapy 	
 • Clinical success 	
 • Success

 • Persistence of signs and symptoms of infection (total cumulative score is >0), reappearance of signs and symptoms, or use of other antimicrobial therapy for the current infection 	
 • Clinical failure 	
 • Failure

 • Refusal to consent to a clinical examination or failed to attend the TOC Visit 	
 • Unable to determine 	
 • Failure

Follow-up Visit		

 Resolution of signs and symptoms of acute cystitis demonstrated at the TOC Visit persist at the Follow-up Visit (total cumulative score is zero) (and no new signs and symptoms) and no use of other antimicrobial therapy 	
 Sustained clinical success 	
 Success

 Resolution of signs and symptoms of acute cystitis at the Follow-up Visit (total cumulative score is zero) and no use of other antimicrobial therapy, but lack of clinical success at the TOC Visit 	
 Delayed clinical success 	
 Failure

 Persistence of signs and symptoms of infection (total cumulative score is >0), reappearance of signs and symptoms, or use of other antimicrobial therapy for the current infection 	
 Clinical failure 	
 Failure

 Signs and symptoms of acute cystitis absent at the TOC Visit re-occur at the Follow-up Visit and no use of other antimicrobial therapy 	
 Clinical recurrence 	
 Failure

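### The endpoint paired with the relapse objective is cumulative non-success at Follow-up, not relapse among TOC successes, and the Follow-up microbiological labels ignore the TOC culture

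*Protocol*

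**What the plan says.** The objective in Protocol section 4, repeated in SAP 2.2, is "To assess the relapse rate (microbiological and clinical) of acute cystitis after treatment with gepotidacin". The only endpoint set against it is "Therapeutic response (combined per-participant microbiological and clinical response) at the Follow-up Visit". Protocol 10.3.3 fixes the denominator: "Therapeutic response (number and percentage of participants with combined per-participant microbiological and clinical response) at the Follow-up Visit for the micro-ITT Population". Therapeutic success needs both microbiological and clinical success, and every other combination is a failure (Protocol 9.1.1, SAP 9.1.1.4).

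Four rules then apply at Follow-up.

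- Microbiological failures carry forward: "Participants considered microbiological failures at the TOC Visit will also be considered microbiological failures at the Follow-up Visit" (SAP Table 6; same rule in Protocol Table 5).
- Clinical failures carry forward: "Participants considered clinical failures at the TOC Visit will also be considered clinical failures at the Follow-up Visit" (Protocol Table 6). SAP Table 7 reaches the same result by giving delayed clinical success a response of failure.
- A missing culture, a missed visit or a withdrawal counts as failure (Protocol Tables 5 and 6; SAP 9.1.1.1 and 9.1.1.3).
- Another antibacterial before Follow-up gives a microbiological outcome of unable to determine and a response of failure.

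Microbiological recurrence at Follow-up is assigned when "A quantitative urine culture taken at the Follow-up Visit shows that the qualifying bacterial uropathogen recovered at Baseline grows" at or above 10^3 CFU/mL. Sustained eradication is assigned when the count is below 10^3. Neither row mentions the TOC culture. Clinical recurrence does look back: "Signs and symptoms of acute cystitis absent at the TOC Visit re-occur at the Follow-up Visit and no use of other antimicrobial therapy".

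**The concern.** Relapse can happen only to someone who was cured first, so a relapse rate needs TOC successes as its denominator and a return of infection as its numerator. The planned endpoint has neither. Its complement pools participants who never responded, participants with missing data, participants treated with something else, and true relapses.

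If that percentage is reported against the relapse objective, a reader could take initial failure and missed visits for late return of infection. Separately, anyone who counts the microbiological recurrence row as relapse would include infections that never cleared.

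**Working it through.** **No stated figure to reproduce.** The documents give no expected relapse rate, target or precision for this objective, so the check has two parts: comparing the definitions, and an illustration on assumed counts.

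**1. Follow-up microbiological labels by TOC result** (Protocol Table 5 and SAP Table 6; baseline pathogen, CFU/mL, no other antibacterial before Follow-up)

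| TOC | Follow-up | Label given | Response in row | Response after carry-forward | What happened |
|---|---|---|---|---|---|
| <10^3 | <10^3 | Sustained eradication | Success | Success | Sustained eradication |
| <10^3 | ≥10^3 | Recurrence | Failure | Failure | Recurrence |
| ≥10^3 | ≥10^3 | Recurrence | Failure | Failure | Persistence |
| ≥10^3 | <10^3 | Sustained eradication | Success | Failure | Late clearance |

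The last two labels are wrong. The same documents condition properly elsewhere. Microbiological recurrence at TOC requires eradication on therapy (Protocol Table 4, SAP Table 5). Clinical recurrence at Follow-up requires absence of symptoms at TOC (Protocol Table 6, SAP Table 7).

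**2. Clinical rows at Follow-up.** Reappearance of signs and symptoms is listed under clinical failure and also defines clinical recurrence. A participant who is symptom-free at TOC, symptomatic at Follow-up and not re-treated meets both rows. If she is re-treated before Follow-up, she is excluded from clinical recurrence and is microbiologically undeterminable, so she enters neither recurrence row.

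**3. Endpoint against relapse rate.** Let N be the micro-ITT size, S the TOC therapeutic successes, m the TOC successes with missing Follow-up, and r the relapses. New infections are set to zero. All four are assumptions.

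- Follow-up failure (planned) = [N − (S − m − r)]/N
- Relapse among assessed TOC successes = r/(S − m)
- Drop between visits = (S − S_FU)/S = (m + r)/S, where S_FU = S − m − r is the number of Follow-up successes

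With N = 20, S = 16, m = 1 (95% Clopper-Pearson intervals):

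| r | Follow-up failure | Relapse | Drop |
|---|---|---|---|
| 0 | 5/20 = 25.0% (8.7 to 49.1) | 0/15 = 0% (0 to 21.8) | 1/16 = 6.25% |
| 2 | 7/20 = 35.0% (15.4 to 59.2) | 2/15 = 13.3% (1.7 to 40.5) | 3/16 = 18.75% |

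With r = 0, TOC success of 60%, 80% or 90%, and m from 0 to 2, Follow-up failure runs from 10% (2/20) to 50% (10/20) for N = 20, and from 10% (1/10) to 60% (6/10) for N = 10. True relapse is zero throughout.

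**4. Why the drop is an upper bound.** Carry-forward makes Follow-up successes a subset of TOC successes. Then (m + r)/S − r/(S − m) = m(S − m − r)/[S(S − m)], which is never negative. The drop also absorbs new infections and re-treatment.

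**The case against.** The strongest reply is that the information is largely there. Therapeutic success is summarised at both visits (SAP 9.1.1.4, display Table 2.7), so the drop between them bounds relapse. Clinical recurrence is a category of its own in display Table 2.6, and Listings 12, 14 and 16 allow participant-level reading at this sample size. A reader might infer that relapse goes wholly unestimated or that the objective cannot be answered. The documents do not support that. What stands is that no document plans the bound, that it mixes relapse with missing data, re-treatment and new infection, and that Tables 2.1 (micro-ITT) and 2.6 (ITT) are separate summaries on different populations that cannot be combined into one relapse count.

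A reader might also infer that recurrence is unconditioned throughout. It is not: the fault is confined to the microbiological rows at Follow-up. It affects only pathogens still present at TOC in participants given no other antibacterial before Follow-up, since the rest are unable to determine.

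The apparent clash between the carry-forward header and the success response for late clearance can be read as the header taking precedence. On that reading therapeutic response is unaffected and only the label is wrong.

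Counting missing as failure and carrying failures forward are deliberate, conservative choices for a success rate; SAP 2.1 cites FDA guidance for its handling of an undetermined TOC clinical result. They are reasonable for that purpose but do not turn the result into a relapse rate.

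**Conclusion.** The point holds as a mismatch between objective and endpoint, plus two labelling faults. Follow-up therapeutic response is not a relapse rate, and none is planned among TOC successes. Follow-up microbiological recurrence and sustained eradication are not tied to the TOC culture. Clinical failure and clinical recurrence overlap.

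The size is illustrative only. With no relapse at all, the planned endpoint shows 10% to 60% failure over the assumed ranges (N of 10 or 20, TOC success 60% to 90%, 0 to 2 missing). A reader might infer that the reported figure would mostly reflect initial failure and missing visits. That depends on TOC success and missingness, for which the documents give no expected values.

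Importance is low to moderate. The objective is exploratory in a PK study with no hypothesis test, no primary or secondary endpoint is touched, and any relapse estimate will be imprecise at this size.

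**What to change.** 1. Keep therapeutic response at Follow-up as planned and add one participant-level line: among TOC therapeutic successes, the proportion with relapse by Follow-up, with a Clopper-Pearson interval. Define relapse as any of: microbiological recurrence (baseline pathogen below 10^3 CFU/mL at TOC and at or above 10^3 at Follow-up), clinical recurrence, or another antimicrobial for the current infection after TOC. Without the third element, a relapse re-treated before Follow-up would be counted as no relapse.
2. Report missing Follow-up and new infections separately. Give the estimate once excluding missing and once counting missing as relapse.
3. In SAP Table 6, split the rows by TOC result. Positive at both visits is persistence (failure). Positive at TOC and then below 10^3 is delayed eradication (failure, in line with the header). Sustained eradication and recurrence both require eradication at TOC. A missing TOC culture meets none of these and needs its own row, with response failure.
4. In SAP Table 7, assign reappearance after TOC success to clinical recurrence only, so that the two clinical rows are mutually exclusive.

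Record the departure from Protocol Tables 5 and 6 in SAP 2.1. The cost is table wording and one summary line, with no new data and no change in sample size.
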